Design overview. Groups of 3-5 clinicians were recruited by each agency leader. Once all clinicians at an agency were enrolled, they had a 2-week initial training period in which they completed the Project ImPACT Beginner e-Course, a 6-hour self-directed online tutorial on Project ImPACT intervention content. The Beginner e-Course consisted of didactic modules with slides and audio recordings about Project ImPACT NDBI intervention strategies and best practices for collaborating with parents. Modules included video examples of caregivers implementing the intervention strategies and periodic quizzes about course content, but did not include explicit instruction about parent coaching.

Following the initial training period, clinicians entered the Baseline Phase (3 to 9 weeks; randomized by agency) during which they were asked to follow the Project ImPACT coaching manual and meet weekly with their enrolled families, but did not receive consultation support. After the baseline phase, all enrolled clinicians at each agency entered the consultation phase, during which they received 12 group consultation sessions, once per week, for 1.5 hours per session. The consultation phase included three, 4-week blocks in which the group completed one consultation training activity per block (i.e., case support, skill rehearsal, or feedback on

videotaped sessions). Clinicians submitted recordings of all Project ImPACT telehealth sessions throughout the Baseline and Consultation phases, and then again at Follow Up (8-weeks post consultation). Information about the procedures used in each phase is outlined below.

Baseline phase. Clinicians received an e-book copy of the Project ImPACT Coaching Manual, which includes detailed descriptions about the theoretical underpinnings of the intervention and lesson plans for each of the 24 sessions (e.g., session agendas, handouts, access to video models of NDBI intervention strategies, examples of trouble-shooting tips for common challenges with clients). Clinicians also received an e-book copy of the Project ImPACT Parent Manual, which includes descriptions of the NDBI strategies in parent-friendly language and tips about how to apply NDBI strategies at home and in the community. Clinicians were instructed to follow the lesson plans in the Project ImPACT coach manual and no consultation support was provided during the Baseline phase.

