spent in role plays). This measure has not been empirically tested, but was used to understand the level of experimental control in the study (i.e., extent to which only one consultation component was delivered in a given phase). Items were rated as Observed (1), Not Observed (0), or Not Applicable. Example items for the Feedback condition include: consultant asked each trainee to introduce their clip prior to screensharing it, consultant prompted each trainee to provide specific praise/constructive feedback about each clip shown, consultant provided specific praise/constructive feedback after each clip. Example items for the Skill Rehearsal condition include: each trainee present at the session completed at least 1 role play scene, consultant asked trainees to self-reflect on clinician performance in role play scenes using the reflection worksheet, scene A was completed. Example items for the Case Support condition include: consultant asked the group of trainees to provide potential solutions to the implementation challenge, consultant provided additional potential solutions to the implementation challenge. Coders also noted timestamps for various activities to determine the amount of time spent on activities of note (e.g., amount of time providing performance feedback).

Five agencies completed all 12 consultation sessions, while one agency completed only 6/12 sessions before all clinicians withdrew from the study. One video recording was corrupted and was unable to be scored; thus, there was a total of 65 consultation sessions that could be coded. Coders needed to meet training criteria of 3 videos in a row with 80% of all items in exact agreement with the master coder. Monthly meetings with the coding team were held in which all members independently coded a video, and the group compared their scores to the master codes and discussed discrepancies. Coders were randomly assigned consultation sessions to score. Ten of the 65 sessions (15%) were rated by both raters to calculate inter-rater reliability. Intraclass correlations were as follows: Feedback = 0.99, Skill Rehearsal = 1.00, Case Support = 1.00.

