mediated interventions (e.g., providing effective in-vivo corrective feedback to caregivers, problem-solving challenges with between-session practice). Subscales included: Collaboration, Demonstration, In-Vivo Feedback, and Reflection and Problem-Solving. Clinically, a score of 4 or 5 for each subscale would be considered “at fidelity.” As this measure is relatively new, no psychometric data has been published yet. All Project ImPACT sessions were randomly assigned to be scored for parent coaching competency by one primary coder naïve to timepoint and condition. Coders needed to meet training criteria of 3 videos in a row with 90% of items within one point of the master codes prior to coding for the actual dataset. Monthly meetings with the coding team were held in which all members independently coded a video, and the group compared their scores to the master codes and discussed discrepancies. Twenty-five percent of Project ImPACT sessions were scored by a second independent coder for reliability. Intra-class correlations ranged from 0.63 to 0.99, indicating moderate to excellent reliability; see Table 7 for all ICCs.

Table 7. Intra-class correlations for each PEACE subscale.

Subscale	Intra-class Correlation
Collaboration	0.69
Demonstration	0.79
In-Vivo Feedback	0.99
Reflection and Problem-Solving	0.63

Data Collection for Questionnaires

During the consultation period, clinicians completed weekly online questionnaires about the following: cancellations/rescheduling information, case penetration (Penetrability Formula), perceptions about Project ImPACT (Perceived Characteristics of Intervention Scale), and perceptions on the usability of that week's consultation training activity (Implementation Strategy Usability Scale). No clinician questionnaires were collected during the 8-week follow up period. After the follow up period, clinicians submitted a final recorded session and set of questionnaires.

Caregivers completed a caregiver-report questionnaire about autism-related challenges (Autism Impact Measure) via online questionnaire at 5 time points: at intake, at the end of each consultation condition (i.e., 4-, 8-, and 12-weeks into the consultation phase), and at the end of the 8-week follow up period.

Measures

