Case penetration. Case penetration was measured via weekly online questionnaires using the Penetrability Formula (Stiles et al., 2002), which uses clinician report of the total number of active Project ImPACT cases divided by the total number of eligible clients on their caseload (i.e., autistic youth under age 6) to yield a percentage. Scores ranged from 0-100.

Penetration was calculated separately for clients with Medicaid insurance and for clients with private insurance or self-pay.

Implementation Strategy Usability Scale. Clinicians reported on the usability of each consultation component weekly across the 4 weeks of each consultation condition using the Implementation Strategy Usability Scale (Lyon et al., 2021), which is an adapted version of the Systems Usability Scale (Brooke, 1996). This 10-item questionnaire uses a 5-point Likert scale to examine clinician perceptions about the complexity of using an implementation strategy (e.g., role plays). Likert scale ratings are used to compute a total usability score, which ranges from 0-100. Internal consistency on the Systems Usability Scale is high, with a mean Cronbach's alpha of 0.91 and a range of 0.83 to 0.97 (J. R. Lewis, 2018).

Perceived Characteristics of Intervention Scale. At baseline, across the consultation period, and at follow-up, clinicians completed the Perceived Characteristics of Intervention Scale (Cook et al., 2015) weekly about their perceptions of Project ImPACT. This 18-item questionnaire includes items related to various constructs from Rogers' Diffusions of Innovation theory (Rogers, 2010): Relative Advantage (i.e., the extent to which the intervention is more effective than other therapies the clinician has used), Compatibility (i.e., the extent to which the intervention fits well with the clinician's clinical judgment and preferences), Complexity (i.e., the extent to which the intervention is clear and easy to use), Trialability (i.e., the extent to which the intervention is easy to try out with clients), Observability (i.e., the extent to which the intervention produces improvements in clients that are easy to see), Potential for Reinvention (i.e., the extent to which the intervention can be adapted to fit the needs of clients and the treatment setting), Task Issues (i.e., the extent to which the intervention improves the quality of the clinician's work), Nature of Knowledge (i.e., the extent to which the knowledge and skills

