Aim 3: Effects of the group consultation model on case penetration and clinician perceptions of Project ImPACT over time. We used two-level multilevel models to examine changes in case penetration and clinician perceptions of Project ImPACT from the Baseline phase to the Consultation phase. Observations (i.e., weekly case penetration data, overall PCIS scores) were nested within clinicians. Questionnaires from all 6 agencies were utilized for this analysis. We ran separate case penetration models for clients using Medicaid insurance and clients using private insurance/self pay.

Due to the fairly homogenous small sample size and concerns about including too many predictors in the model, we did not include clinician demographics/previous training experiences in the multilevel model predicting perceptions of Project ImPACT on the PCIS. However, we were still interested in the relationship between these variables and PCIS scores. Thus, we examined the relationships between PCIS scores averaged for each clinician and a number of provider demographic, training, and caseload variables using Pearson's correlations for interval data and Spearman's rho for ordinal data.

Exploratory Aim 4: Effect of Project ImPACT on child social communication outcomes over time. We fit a series of two-level multilevel models to estimate the extent to which Project ImPACT was associated with changes in parent-reported child social communication outcomes over time. Observations (i.e., caregiver ratings on the Autism Impact Measure) were nested within each child. There were 3 multilevel models in total (Communication, Social Reciprocity,

and Peer Interaction). Questionnaires from families across 5 agencies with sufficient data were utilized for this analysis.

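### Aim 3 correlates clinician characteristics with one PCIS average per clinician, with no stated averaging window and no phase adjustment, so unequal agency schedules can leak into the correlations (minor)

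*Combined protocol and SAP*

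**What the plan says.** The Aim 3 part of the Data Analytic Plan keeps clinician characteristics out of the two-level PCIS model. It gives two reasons: a small, rather uniform sample, and "concerns about including too many predictors in the model". Instead, "we examined the relationships between PCIS scores averaged for each clinician and a number of provider demographic, training, and caseload variables", with Pearson's coefficient for interval data and Spearman's rho for ordinal data. All six agencies contribute.

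On when PCIS was collected, two sections differ. The measure description says "At baseline, across the consultation period, and at follow-up, clinicians completed the Perceived Characteristics of Intervention Scale", on a weekly basis. Data Collection for Questionnaires lists PCIS under "During the consultation period, clinicians completed weekly online questionnaires about the following" and does not mention baseline. It adds "No clinician questionnaires were collected during the 8-week follow up period", followed by one final set of questionnaires afterwards.

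On schedules, Design overview gives a "Baseline Phase (3 to 9 weeks; randomized by agency". Agencies 1-4 drew from 3-6 weeks and agencies 5-6 from 6-9 weeks. The section on the methodological challenge adds one week for agencies 5 and 6. Consultant Fidelity to Consultation Conditions reports that "one agency completed only 6/12 sessions before all clinicians withdrew from the study".

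**The concern.** Specific Aim 3 predicts that perceptions of the intervention improve over time. If they do, an average over all of a clinician's weeks depends partly on the share of those weeks that fall in Consultation. The agency's baseline length and its stopping date set that share, not the clinician's opinion of the intervention. Everyone in an agency has the same schedule, so the resulting shift lines up with any characteristic that differs between agencies. With 3-5 clinicians in each of six agencies (18 to 30 in all), that could create or mask an association.

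The worry about too many predictors explains why the characteristics were not all entered together. It does not explain why phase was left out when each was examined on its own.

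**Working it through.** 1. Reproduction. The plan gives no sample size, effect size or error rate for these correlations. The one stated count that checks the exposure inputs is the number of coded consultation sessions: 5 agencies × 12 + 6 − 1 corrupted recording = 65, which matches the text.

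2. Inputs. Baseline weeks b are 3-6 (agencies 1-4) or 6-9 plus 1, that is 7-10 (agencies 5-6). Consultation weeks c are 12, or 6 at the agency that stopped. The PCIS change d, the PCIS standard deviations (SDs), the exact number of clinicians and the identity of that agency are not given in the text.

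3. Formula. If PCIS steps up by d at the start of Consultation, a clinician's all-weeks average is the baseline level + d × c/(b + c).

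| Schedule | c/(b + c) |
|---|---|
| Completer, b = 3 | 12/15 = 0.80 |
| Completer, b = 6 | 12/18 = 0.67 |
| Completer, b = 7 | 12/19 = 0.63 |
| Completer, b = 10 | 12/22 = 0.55 |
| Stopped at 6, agency 1-4 | 6/9 = 0.67 to 6/12 = 0.50 |
| Stopped at 6, agency 5-6 | 6/13 = 0.46 to 6/16 = 0.375 |

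4. Largest gaps between clinicians with identical perceptions, with points for an assumed d of 0.5 to 1.0 on the 7-point scale:
   - Completers: 0.80 − 0.55 = 0.25d, or 0.13 to 0.25 points.
   - Including the stopped agency, if it is one of 1-4: 0.80 − 0.50 = 0.30d, or 0.15 to 0.30 points.
   - Including it, if it is 5 or 6: 0.80 − 0.375 = 0.425, about 0.43d, or 0.21 to 0.43 points.

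   Counting the completers' one final rating at the consultation level gives 13/16 = 0.81 and 13/23 = 0.57, so the gap stays at about 0.25d.

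5. Which agency stopped. The text reports 20 coded Case Support and 22 coded Skill Rehearsal sessions, which leaves 65 − 42 = 23 for Feedback. Five completing agencies account for 5 × 4 = 20 of each. The excess is 0, 2 and 3, plus one corrupted recording. Six sessions in 4-week blocks must split 4 + 2, so the stopped agency had 4 Feedback (one unscorable), 2 Skill Rehearsal and no Case Support. Aim 1 models all three components and requires replication in all three agencies with sufficient baselines, evidently 2, 5 and 6. The stopped agency is therefore probably 1, 3 or 4, and 0.30d is the relevant ceiling under a step change.

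6. Sensitivity to the time course. Suppose PCIS instead climbs linearly, with d the mean rise over 12 weeks. The stopped agency's six weeks then average 3.5/6.5 = 0.54d. With b = 6 its overall average is 0.50 × 0.54 = 0.27d, a gap of 0.80 − 0.27 = 0.53d from the highest completer. If only consultation weeks were averaged, baseline length drops out. The stopped agency would then be off by 1 − 0.54 = 0.46d under this course, and by nothing under a step.

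7. Effect on the correlations. A simulation with no true association used 6 agencies of 3-5 clinicians, the documented baseline ranges and one randomly chosen agency stopping at 6 weeks. It assumed d of 0.25 to 1.5, a between-clinician SD of 0.5 or 1.0 and a within-clinician SD of 0.5, with 1,500 runs per setting.
   - The artefact took 0.06% to 8% of between-clinician variance under a step, and 0.2% to 20% under a linear course.
   - At a nominal 5%, the false-positive rate was 3.9% to 7.0% in 41 of 48 settings (Monte Carlo error about 0.6 points). The other seven all had d of 1.0 or 1.5 and a characteristic that was partly or wholly constant within agency.
   - For d up to 1.0 the highest rates were 7.5% (step) and 8.8% (linear). For d = 1.5 they were 9.1% and 14.9%.
   - Weighting the two phases equally reduced the artefact to 0 under a step and to 0.05% to 6% of variance under a linear course.

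**The case against.** The strongest reply is that the plan never says all weeks were averaged. The data-collection section ties weekly PCIS to the consultation period. If only those weeks were used, unequal baselines do no harm and only the stopped agency is affected, and only if PCIS trends within Consultation. This stands as a limit, so the point must be conditional. All weeks is still the more natural reading: the Aim 3 model compares Baseline with Consultation, so baseline ratings must exist, and for Aim 2 the plan says explicitly that averaging was by condition.

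Second, baseline lengths were randomised by a statistician unaware of agency characteristics, and nothing shows that caseload or training differed by agency. This also stands in part. However, the split between agencies 1-4 and 5-6 followed later recruitment and was not randomised, and completers' consultation shares do not overlap across it (0.67-0.80 against 0.55-0.63). Withdrawal was not randomised either.

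Third, the plan also cites its small, uniform sample. That is a reason for caution with any of these estimates. But one slope at a time asks no more of 18-30 clinicians than one correlation at a time.

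A reader might also object that clinicians with few ratings count as much as those with many. That is trivial here. With both SDs assumed to be 0.5 and independent errors, the variance of a clinician mean is 0.25 + 0.25/9 = 0.278 with 9 ratings and 0.25 + 0.25/22 = 0.261 with 22, about 6% apart.

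**Conclusion.** The point holds conditionally and is minor. The averaging window is unstated and no phase adjustment is described. If all weeks are averaged and PCIS steps up by d, schedule alone can separate identical clinicians by up to 0.25d among completers and probably about 0.30d overall. These are worst-case pairs, not typical differences. The 0.30d figure rests on the inference from session counts and on a step change; a steady climb through Consultation would widen the gap for the stopped agency. If d is zero there is no artefact.

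A reader might infer that every correlation is materially distorted, or that 0.43d is the size to expect. The documents support neither. A characteristic unrelated to agency mainly picks up noise, simulated false-positive rates stay close to nominal in most settings, and 0.43d requires the stopped agency to be 5 or 6. Nor is the main Aim 3 result in doubt: the two-level model compares the phases directly and does not use these averages. The correlations carry no stated hypothesis.

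**What to change.** State which weeks enter the PCIS average, and reconcile Data Collection for Questionnaires with the PCIS measure description on whether weekly ratings were collected at baseline. Then do one of the following and label the results exploratory:

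- Enter each characteristic on its own as a clinician-level predictor in the existing two-level PCIS model with phase, and report each slope with its 95% interval.
- Correlate phase-specific or phase-adjusted clinician means. This keeps Spearman's rho for the ordinal variables.

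The cost is a few extra runs of an existing model or a recalculated mean. Under the first option the results become adjusted slopes rather than coefficients. Neither option fully removes distortion from the agency that stopped early if PCIS trends within Consultation, so that limit should be stated.

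### Exploratory Aim 4 leaves out one of six agencies under an undefined, data-dependent sufficiency rule that its two-level models do not need

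*Combined protocol and SAP*

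**What the plan says.** The Data Analytic Plan, under Exploratory Aim 4, describes three two-level models (Communication, Social Reciprocity, Peer Interaction) with caregiver ratings on the Autism Impact Measure nested within child. It closes with: "Questionnaires from families across 5 agencies with sufficient data were utilized for this analysis". No threshold, reason, agency number, count of children or missing-data assumption is given.

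For Aim 2 and again for Aim 3 the same plan says: "Questionnaires from all 6 agencies were utilized for this analysis".

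Under Data Collection for Questionnaires, caregivers rate the child "via online questionnaire at 5 time points": intake, the end of each of the three consultation conditions (4, 8 and 12 weeks), and the end of the 8-week follow-up.

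Under Consultant Fidelity to Consultation Conditions: "Five agencies completed all 12 consultation sessions, while one agency completed only 6/12 sessions before all clinicians withdrew from the study".

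**The concern.** Whether an agency has sufficient data is known only after enrolment, so the rule selects families on what happened during the study. If an agency's data ran short for reasons related to how the programme was going, the remaining families are a selected group, and the Aim 4 result describes families whose agency continued. The reader cannot judge this, because neither the rule nor the numbers it removes are given.

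The restriction also sits oddly with the rest of the plan. Aim 1 is limited to three agencies for a stated reason (too few usable baseline sessions, explained under the methodological challenge with the baseline phase). Aim 4 has no such explanation. Aim 2 uses a repeated measures ANOVA across three conditions and still reports all six agencies, although an agency that stopped after 6 sessions cannot have reached its third 4-week block. Aim 4 uses a method that tolerates partial series, yet it is the aim that drops an agency.

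The Autism Impact Measure is the only child outcome described, so the selection falls on the only evidence about children.

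**Working it through.** The plan gives no sample size, power or effect size for Aim 4, so there is no such figure to reproduce. The checks below use its counts and schedule, plus assumptions labelled as such.

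**1. Agency counts.** Five agencies with 12 sessions, one with 6, one corrupted recording: 5 × 12 + 6 − 1 = 65. This agrees with "there was a total of 65 consultation sessions that could be coded". A five/one split therefore exists in the document, and it has the same shape as the Aim 4 restriction.

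**2. Ratings due if the withdrawn agency is the one left out.** Each condition is 4 weekly sessions, so 6 sessions are one complete condition plus 2 sessions of the next. Of the five rating points (intake, 4, 8, 12 and 12 + 8 = 20 weeks), intake and 4 weeks had fallen due: 2 of 5 at most. The document does not say whether those questionnaires were returned.

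**3. Whether the model needs complete series.** Assume 4 children per agency, with one agency cut to 2 of 5 points. Keeping it gives 20 × 5 + 4 × 2 = 108 ratings from 24 children; dropping it gives 100 from 20. On simulated data of this shape a random-intercept model converges in both cases. Partial series are no obstacle.

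**4. What selection could amount to if every family had been followed.** Let s be the excluded agency's share of families and r its mean change relative to the retained agencies. The five-agency mean overstates the all-family mean by 1/[(1 − s) + s·r] − 1. Taking families as proportional to clinicians (3 to 5 per agency), s lies between 3/28 and 5/20.

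| s | r = 0 | r = 0.5 | r = 1 |
|---|---|---|---|
| 3/28 = 10.7% | 12.0% | 5.7% | 0% |
| 1/6 = 16.7% | 20.0% | 9.1% | 0% |
| 5/20 = 25% | 33.3% | 14.3% | 0% |

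Nothing in the document fixes s or r.

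**5. What refitting to existing data would change.** Assume s = 1/6, r = 0, equal intake means, ratings at intake and 4 weeks only in the sixth agency, categorical time, and a random intercept with within-child correlation ρ. Write d4 and d12 for the retained agencies' mean change at 4 and 12 weeks.

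- At 4 weeks the estimate falls by s·d4, which is 1/6 = 16.7% of d4.
- At 12 weeks the model predicts the missing ratings from the two observed ones. Each carries weight ρ/(1 + ρ), so the estimate falls by s·d4·ρ/(1 + ρ).
- If change builds up linearly to 12 weeks, d4 = d12/3. The fall in d12 is 1/6 × 1/3 × ρ/(1 + ρ): 1.9% at ρ = 0.5, 2.3% at ρ = 0.7, 2.6% at ρ = 0.85.
- If all the change had come by 4 weeks (d4 = d12), the fall is 1/6 × ρ/(1 + ρ): 5.6%, 6.9% and 7.7%.
- With a single linear time term and linear build-up to 12 weeks, the simulated shift is under 1%.

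**The case against.** The best defence is that the sentence may simply report what was available. Ratings that were due are not ratings that were received. If the sixth agency's families returned only intake forms, or none, including them adds almost nothing about change. The restriction is disclosed, the aim is exploratory and uncontrolled, and model parameters are deferred to a Results section not included here. Refitting with at most two early ratings per family would barely move the 12-week estimate, and if dropout depends on unseen outcomes a likelihood-based model on partial data does not repair it.

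Most of this stands, and it limits the size of the point. It does not justify leaving the rule undefined or the counts unreported, and it gives no reason to withhold an all-available-data fit.

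A reader might also infer three stronger things that the document does not support:

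- That individual children whose follow-up stopped early were removed. The stated restriction concerns agencies. Nothing says that incomplete series within the five retained agencies were dropped, and the phrase about sufficient data could qualify families or agencies.
- That the agency left out is the one that withdrew. The matching five/one split makes this reasonable, but the agency is not named.
- That the exclusion favours the predicted improvement, by some 20%. No reason for the withdrawal is given. Competing demands on providers' time, which the introduction lists as a barrier, need not relate to child outcome. The 20% is one cell of the table above and requires full follow-up with no change at all in the excluded families.

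**Conclusion.** The point holds in a limited form. Aim 4 excludes one of six agencies under an undefined rule that depends on the data obtained, the other questionnaire-based aims keep all six, and the chosen models do not require the exclusion. That is a possible selection which the plan could remove, or at least show, at little cost.

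Its effect on the result cannot be derived, because the document gives no number of families, no returns and no reason. If the excluded agency is the withdrawn one, and if its families returned both ratings due and showed no change, the refit would mainly affect the 4-week estimate (16.7% lower with equal agency sizes). The 12-week estimate would fall by about 2 to 3% under linear build-up, or up to 7.7% if all change had come by 4 weeks. If those families changed as the others did, the expected shift is zero. Given the exploratory status of the aim, this is a worthwhile correction and does not by itself overturn the Aim 4 result.

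**What to change.** - Fit the three Aim 4 models to every child with at least one caregiver rating from all six agencies.
- State the assumption this rests on: ratings are missing at random given the observed ones. In plain terms, children without later ratings would have gone on like children with similar earlier ratings.
- Keep the five-agency fit as a sensitivity analysis, and define the sufficiency rule behind it.
- Report how many families and ratings that rule excluded, and from which agency (by number).
- If the excluded agency supplied no ratings after intake, say so and limit the Aim 4 conclusion to families in the five agencies with data.

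The cost is a little more analysis of data already held. Data collection is reported as finished, so no further questionnaires are involved. The estimate may become slightly less favourable, mainly at 4 weeks.
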